## 7.5 Pharmacokinetics

The timing of sampling for PK analysis is based on available steady-state data from RA patients treated with 40 mg adalimumab s.c. These data showed that adalimumab steady-state concentrations were reached approximately 20 weeks after the beginning of adalimumab treatment ([60, 61](#)). Sparse sampling for population PK analysis will be collected in a subset of patients (at least 30/arm) in this trial.

All patients will have PK samples taken pre-first dose, and then prior to dosing on Weeks 2, 4, 12, 24, 36, and 52. In addition, a subset of 60 patients (30 per arm) will have additional samples to support the population PK analysis taken on Days 2 (24 h post first dose), 4, and 9, and Days 2 (24 h post Week 24 dose), 4, 9, and 14 (Week 26 pre-dose) after the Week 24 dose (see [Table 2](#)).

## 7.6 Biomarkers

Not applicable.

## 7.7 Other Assessments

Patient-reported outcomes (PROs) and the Physician's Global Assessment of Disease Activity will be assessed at the visits indicated in [Table 1](#). The PROs consist of the HAQ-DI, Patient's Global Assessment of Disease Activity, Patient's Assessment of Arthritis Pain, SF-36, and EQ-5D-5L dimension instruments. The PRO/QoL questionnaires and the Physician's Global Assessment of Disease Activity are recommended to be completed prior to any of the other trial-related assessments being performed, that is, physical examinations, blood draws, trial treatment administration, etc. Data will be collected by the Contract Research Organization (CRO) and housed in a database. Validated translated versions of the PROs/QoL questionnaires will be used for each country participating in this trial

### 7.7.1 HAQ-DI

The HAQ-DI is a patient-reported questionnaire that is commonly used in RA to measure disease associated disability (assessment of physical function). It consists of several questions referring to 8 domains: dressing/grooming, arising, eating, walking, hygiene, reach, grip, and activities (62, 63).

The disability section of the questionnaire scores the patient's self-perception on the degree of difficulty (0 = without any difficulty, 1 = with some difficulty, 2 = with much difficulty, and 3 = unable to do) covering the following domains: dressing and grooming, arising, eating, walking, hygiene, reach, grip, and performing other daily activities. The reported use of special aids or devices and/or the need for assistance of another person to perform these activities is also assessed. The scores for each of the functional domains will be averaged to calculate the functional disability index.

### 7.7.2 Visual Analog Scales

Visual analog scales will include the Patient's and Physician's Global Assessment of Disease Activity, Patient's Assessment of Arthritis Pain and injection site pain.

#### Patient's Global Assessment of Disease Activity

The patient's overall assessment of his or her arthritis during the last 24 hours will be recorded using the horizontal VAS where the left end represents no disease activity (symptom free and no arthritis symptoms) and the right end represents maximum disease activity (maximum arthritis disease activity).

The patient will be asked to give an overall assessment of how the arthritis is affecting him/her at present by marking a vertical tick on a VAS from "no arthritis activity" to "extremely active arthritis."

#### Physician's Global Assessment of Disease Activity

The physician's overall assessment of the patient's arthritis during the last 24 hours will be recorded using the horizontal VAS where the left end represents no disease activity (symptom free and no arthritis symptoms) and the right end represents maximum disease activity (maximum arthritis disease activity).

The physician will give an overall assessment of how the arthritis is affecting the patient at present by marking a vertical tick on a VAS from "no arthritis activity" to "extremely active arthritis."

#### Patient's Assessment of Arthritis Pain

The patient will be asked to assess his or her current level of pain by marking a vertical tick on a horizontal VAS with the left end marked as "no pain" and the right end marked as "worst possible pain." The scale should be administered prior to the tender and swollen joint count examination.

## Injection Site Pain

The patient's reported perception of pain will be measured on a VAS where the slash drawn by the patient represents pain of increasing intensity. The first 2 injections will be administered by qualified personnel. The next three doses of IMP (3-5) will be self-administered by the patient and injection site pain will be assessed. Pain will be recorded immediately after, 15 minutes after, and 1 hour after the injections received by the patient.

Results will be expressed in millimeters measured between the left end of the scale and the crossing point of the vertical line of the tick. This procedure is applicable for all VAS scales used in the trial.

### 7.7.3 SF-36

Patients will complete the SF-36 v2, standard version, a generic, health survey consisting of 36 questions, yielding 8 health-related quality of life (HRQoL) domains (physical functioning, role-physical, bodily pain, general health, vitality, social function, role emotional, mental health) as well as a psychometrically based physical component score (PCS) and mental component score (MCS).

### 7.7.4 EQ-5D-5L

Patients will complete the EQ-5D, a standardized measure of health status. It consists of 5 questions (mobility, self-care, usual activity, pain/discomfort and anxiety/depression) - the EQ-5D descriptive system, rated on a 5-point scale (no problems, slight problems, moderate problems, severe problems and unable to/extreme problems) and a health state VAS of 0 (Worst imaginable health state) to 100 (Best imaginable health state).

## 8 Statistics

### 8.1 Sample Size

According to EMA recommendation (EMA/CHMP/SAWP/200743/2016), a total of 100 patients/arm should be adequate for a study primarily focusing on safety. To account for drop outs, this descriptive study will include 260 randomized patients in total (130/arm) in order to ensure 200 subjects in the study at Week 52. In fact, based on averaged originator's dropout rates at Week 52, a 20% rate of drop-out overall is included in the sample size (29, 40, 41). This sample size will permit an informative assessment of the occurrence of most common AESI (> 1/10) such as injection site reactions, and rash with a precision of 12.0% and 9.0% for the AESIs incidence of 26.0% and 11.0% respectively (29).

A subset of 60 patients (30 per treatment arm) will be randomly selected to participate in population PK analysis.

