## 5.2.3 Rationale for Endpoints

### 5.2.3.1 Primary Endpoint

#### Incidence of AESI (Hypersensitivity) including and up to Week 52

In order to provide long-term safety and immunogenicity data in patients to support the new CCI formulation, this descriptive study will evaluate the safety and immunogenicity profile of MSB11022-CCI compared to the Humira® in patients with moderately to severely active RA who have had an inadequate response to MTX. In such a population, the rate of most commonly observed hypersensitivity events is 26.5% for the injection site reactions and 11% for rash (29).

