### 8.4.4 Safety

The Safety Analysis Set will include all randomized patients who receive at least one dose of trial treatment. Patients will be analyzed according to the actual treatment they receive during the trial.

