7.1 Sample Size

According to the European Medicine Agency (EMA) recommendation (EMA/CHMP/SAWP/200743/2016), a total of 100 patients/arm should be adequate for a study primarily focusing on safety. To account for drop outs, this descriptive study will include 260 randomized patients in total (130/arm) in order to ensure 200 subjects are in the study at Week 52. In fact, based on averaged originator's dropout rates at Week 52, a 20% rate of drop-out overall is included in the sample size calculation (1, 2, 3). This sample size will permit an informative assessment of the

occurrence of most common AESIs (> 1/10) such as injection site reactions and rash with a precision of 12.0% and 9.0% for the AESI incidence of 26.0% and 11.0% respectively (0).

A subset of 60 patients (30 per treatment arm) will be randomly selected across all sites to participate in population PK analysis.

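### The stated AESI precision of 12.0% and 9.0% matches about 100 to 104 patients per arm, not the roughly 130 per arm in the Safety set on which AESIs are analysed

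*Protocol*

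**What the plan says.** Protocol 8.1 starts from a regulatory recommendation that "a total of 100 patients/arm should be adequate for a study primarily focusing on safety". It then randomises 260 patients (130 per arm) "in order to ensure 200 subjects in the study at Week 52" and adds that "a 20% rate of drop-out overall is included in the sample size". The next sentence says that this size gives an informative assessment of the commonest AESIs, injection site reactions and rash, "with a precision of 12.0% and 9.0% for the AESIs incidence of 26.0% and 11.0% respectively". The statistical methods part of the synopsis attaches the same two figures to the sample size, and SAP 7.1 repeats them: "precision of 12.0% and 9.0% for the AESI incidence of 26.0% and 11.0% respectively".

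For the analysis, Protocol 8.5.2 and SAP 15.1 place the primary AESI endpoint in the Safety set. Protocol 8.4.4 defines that set: "The Safety Analysis Set will include all randomized patients who receive at least one dose of trial treatment". Both analysis sections plan to report the half-width of the 95% CI for the between-arm difference in the commonest AESIs.

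For the planning rate, Protocol 5.2.3.1 says that the rate of the most common hypersensitivity events "is 26.5% for the injection site reactions and 11% for rash". Section 8.1 uses 26.0% for the first of these and cites the same published 52-week placebo-controlled adalimumab trial.

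**The concern.** The precision sentence directly follows the statement of 260 patients and the dropout allowance, so its natural subject is 130 per arm. The two percentages look too wide for 130 per arm. Dropout does not explain the gap, because a patient who takes one dose and later leaves still counts in the Safety set. Protocol 5.2 and 8.4.3 say so expressly for patients stopped as non-responders.

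The trial is descriptive, with no hypothesis test or margin, so the expected interval width is the main computed property that a reader can hold against the results. The observed half-width is itself a planned output. If the planned figure belongs to a different denominator, comparing the two misleads.

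**Working it through.** **Inputs**
- Two-sided 95% interval, z = 1.96 (SAP 11.1); 1:1 allocation (Protocol 8.2).
- Rates 26% and 11% (Protocol 8.1), taken as equal in both arms.
- Patients per arm: 100 (the Week 52 target, 200/2), 104 (130 × 0.8, after the stated 20% dropout), and 130 (Safety set, if nearly all randomised patients are dosed).
- Precision taken as the half-width of the CI for the between-arm difference (Protocol 8.5.2, SAP 15.1).

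**Formulas**
- Wald: h = z × √(2p(1−p)/n).
- Newcombe with equal observed rates: h = √((p−l)² + (u−p)²), where l and u are the Wilson limits, [p + z²/2n ± z√(p(1−p)/n + z²/4n²)] / (1 + z²/n).

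**Reproducing the plan's figures, 100 per arm**
- Wald at 26%: 1.96 × √(2 × 0.26 × 0.74/100) = 12.16 points.
- Wald at 11%: 1.96 × √(2 × 0.11 × 0.89/100) = 8.67 points.
- Newcombe: 12.06 and 8.99 points.

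**The same at the Safety set size, 130 per arm**
- Wald at 26%: 1.96 × √(0.3848/130) = 10.66 points.
- Wald at 11%: 1.96 × √(0.1958/130) = 7.61 points.
- Newcombe: 10.60 and 7.82 points.

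| Per arm | Wald, 26% / 11% | Newcombe, 26% / 11% | Whole percents |
|---|---|---|---|
| 100 | 12.16 / 8.67 | 12.06 / 8.99 | 12 / 9 |
| 104 | 11.92 / 8.50 | 11.83 / 8.80 | 12 / 9 |
| 115 | 11.34 / 8.09 | 11.26 / 8.35 | 11 / 8 |
| 130 | 10.66 / 7.61 | 10.60 / 7.82 | 11 / 8 |

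**Other readings at 130 per arm**
- Miettinen-Nurminen gives 10.70 / 7.89 and Agresti-Caffo 10.63 / 7.72.
- Wald with a 1/n continuity correction gives 11.43 / 8.38.
- A 90% interval gives 8.95 / 6.38.
- A single-arm Wald half-width is 7.54 / 5.38.

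None of these gives 12 and 9.

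**Gap between stated and expected**
- At 26%: 12.0 − 10.60 = 1.40 (Newcombe) and 12.0 − 10.66 = 1.34 (Wald).
- At 11%: 9.0 − 7.82 = 1.18 (Newcombe) and 9.0 − 7.61 = 1.39 (Wald).

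**Effect of the planning rate**
Using 26.5% in place of 26.0% at 130 per arm moves Newcombe from 10.60 to 10.66 and Wald from 10.66 to 10.73, under 0.1 point.

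**The case against.** The strongest reply is that the sentence refers to the 200 patients secured at Week 52. Section 8.1 opens with 100 per arm and builds dropout into the number, and at 100 per arm the stated pair is right to whole percents. On that reading there is no miscalculation, only a denominator left unsaid. This is fair, and it is why the point is a mismatch between the precision and the analysis set rather than faulty arithmetic. It does not remove the need for a correction, because the primary endpoint is not analysed in completers.

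Four stronger inferences are tempting, and the documents do not support them:
- *That the trial is mis-sized.* The number rests on the cited recommendation of 100 per arm plus a dropout allowance. The precision is reported as what that number delivers. It is not what the number was solved from, and the discrepancy runs in the safe direction.
- *That the sponsor used the Newcombe method with 100 per arm.* Wald and Miettinen-Nurminen (12.20 / 9.09) at 100 also round to 12 and 9, as do Wald and Newcombe at 104. The method cannot be identified. SAP 15.2.1 names Newcombe for the ACR20 difference only. For AESIs, SAP 15.1 names Clopper-Pearson within each arm and no method for the difference.
- *That the plan never says the quantity is a between-arm difference.* Section 8.1 and SAP 7.1 do not, but the synopsis, Protocol 8.5.2 and SAP 15.1 all name that half-width as an output.
- *That a decision will go wrong.* No margin, test or rule uses 12.0% or 9.0%, and the reported intervals will come from the observed data.

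**Conclusion.** The concern holds as a mismatch between a stated precision and the set it should describe. The published 12.0% and 9.0% belong to about 100 to 104 patients per arm. With about 130 per arm in the Safety set, the expected half-widths are 10.6 to 10.7 points at 26% and 7.6 to 7.8 points at 11%. The plan understates its own precision by about 1.2 to 1.4 points, and the sample size stands.

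This rests on three assumptions: equal rates in the two arms, precision meaning the half-width of the two-sided 95% CI for the difference, and nearly all randomised patients receiving a dose. The last is not critical. If 15 per arm were never dosed, 115 would remain and the half-widths would be 11.3 and 8.1 to 8.4 points, still short of 12 and 9. Early departure shortens follow-up and could lower the observed incidence, but it does not shrink this denominator. The 26.0% versus 26.5% discrepancy is editorial.

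**What to change.** In Protocol 8.1, the synopsis and SAP 7.1:
- Define precision as the half-width of the two-sided 95% CI for the between-arm difference in incidence.
- State that with about 130 per arm in the Safety set it is about 10.6 to 10.7 points at 26% and 7.6 to 7.8 points at 11%, and that it would be about 12 and 9 points if only 100 per arm contributed.
- Name the interval method behind the figures, so that one value can replace each range. The choice is the sponsor's. Naming the same method in SAP 15.1 for the AESI difference would let planned and observed widths be compared directly.
- Use one planning rate for injection site reactions, 26.0% or 26.5%, here and in Protocol 5.2.3.1.

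The cost is a wording change in these places, with no effect on patients, visits or the planned analyses.

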## 8.2 Randomization

Eligible patients will be randomized in permuted blocks in a 1:1 ratio by an IWRS to receive either MSB11022-**CCI** s.c. or Humira® s.c. at a dose of 40 mg every other week starting at baseline up to and including Week 48.

Randomization will be stratified by previous disease-modifying therapy use. Patients will be stratified by the type of systemic therapy previously received: non-biological (biologic naïve patients) versus biological (biologic experienced patients). Patients who previously received both (biological and non-biological systemic therapies) will be assigned to the “biological” group. The exposure to previous biological agents will be limited to 1 TNF inhibitor other than adalimumab. The participation of patients in the previous biological systemic therapy stratum will be capped at 20% of the total number of patients randomized. This is in accord with what registered in other trials with biological agents in different rheumatic indications (64, 65, 66).

## 8.3 Endpoints

### 8.3.1 Primary Endpoint

- Safety
  - Incidence of AESIs including and up to Week 52 (AEs will be recorded at each visit: screening, baseline [Week 0], and Weeks 2, 4, 8, 12, 24, 36, 48, and 52)

### 8.3.2 Secondary Endpoints

#### Key Secondary Endpoint

- Efficacy
  - ACR20 at Week 12

#### Other Secondary Endpoints

- Safety
  - Occurrences of TEAEs and SAEs including and up to the 4-month Safety Evaluation visit (AEs will be recorded at each visit: screening, baseline [Week 0], and Weeks 2, 4, 8, 12, 24, 36, 48, and 52, and 4-week and 4-month Safety Follow-up)
  - Vital signs at screening, baseline and at Weeks, 2, 4, 8, 12, 24, 36, 48, and 52
  - Physical examination at screening, baseline and at Weeks 2, 4, 8, 12, 24, 36, 48, and 52
  - Hematology, urinalysis and biochemistry analysis at screening, baseline and at Weeks 2, 4, 12, 24, 36, 48, and 52
  - ANA and anti-dsDNA at baseline and at Weeks 24 and 52
  - 12-lead ECG at screening, Weeks 12, 24, and 52

- Immunogenicity
  - ADA to adalimumab and ADA titer including and up to Week 52
  - Neutralizing ADA to adalimumab including and up to Week 52
- Efficacy
  - ACR20 at Weeks 2, 4, 8, 24, and 52
  - ACR50 response rates at Weeks 2, 4, 8, 12, 24, and 52
  - ACR70 response rates at Weeks 2, 4, 8, 12, 24, and 52
  - Change from baseline in DAS28-ESR to Weeks 2, 4, 8, 12, 24, and 52
  - Proportion of patients with DAS28 low disease activity and remission at Weeks 2, 4, 8, 12, 24, and 52
  - Change from baseline in SDAI at Weeks 2, 4, 8, 12, 24, and 52
  - Change from baseline in CDAI at Weeks 2, 4, 8, 12, 24, and 52
  - ACR/EULAR Boolean remission rates at baseline, Weeks 2, 4, 8, 12, 24, and 52
- Quality of Life (QoL) and Physical Function
  - At baseline, then at Weeks 12, 24, and 52:
    - HAQ-DI - Health Assessment Questionnaire – Disability Index
    - SF-36 - 36-item Short-Form Health Survey
    - EQ-5D-5L - The EuroQoL-5D-5L dimension instrument
  - Injection site pain
    - Mean change in injection site pain on a VAS, evaluated during 3 (doses 3-5) administrations of IMP

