**Other secondary endpoints**

**Safety**

- Occurrences of treatment-emergent adverse events (TEAEs) and serious adverse events (SAEs) including and up to Week 52
- Clinical laboratory values including hematology, chemistry, and urinalysis
- Vital signs
- Physical exam
- 12-lead electrocardiogram (ECG)

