### 5.2.3.3 Other Secondary Endpoints

#### Safety

#### **Incidence of TEAEs and SAEs including and up to Week 52**

In a population of MTX insufficient responders, the rate of TEAEs and SAEs at Week 52 has been reported up to 91% and 15-17%, respectively (40, 41, 42).

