7.2 Randomization

Eligible subjects will be randomized in permuted blocks in a 1:1 ratio by an IWRS to receive either MSB11022-CCI sc or Humira sc at a dose of 40 mg every other week starting at baseline up to and including Week 48.

Randomization will be stratified by previous disease-modifying therapy use. Subjects will be stratified by the type of systemic therapy previously received: non-biological (biologic naïve subjects) versus biological (biologic experienced subjects). Subjects who previously received both (biological and non-biological systemic therapies) will be assigned to the "biological" group. The exposure to previous biological agents will be limited to one TNF inhibitor other than adalimumab. The participation of subjects in the previous biological systemic therapy stratum will be capped at 20% of the total number of subjects randomized.

8 Overview of Planned Analyses

Once the last subject has completed the 4-month safety follow-up visit, the database will be locked. The analysis will be performed using cleaned study data collected in electronic case report form (eCRF) or transferred from laboratories performing laboratory tests and biosample analysis until the date of the 4-month safety follow-up visit of the last subject. Once the data cleaning is complete, a data review meeting will be held prior to the database lock. In addition, no data can be frozen or locked and no randomization code should be unblinded until this Statistical Analysis Plan (SAP) has been approved.

The final analysis will include all data collected during the study up to week 52 date (or end of treatment date+28 days, whichever occurs later) for subjects who completed the study, and theoretical week 52 (ie 52 weeks after first intake) or 4 months safety follow-up visit, whichever occurs first, for subjects who early terminated the treatment.

All AE tables and listings will be re-produced to reflect any additional AEs and any updates to the reported AEs in final analysis. Additionally the concomitant medication and procedure tables and listings will be re-produced to reflect any updates.

In addition, an independent data monitoring committee (IDMC) will review safety and tolerability data of this study on an ongoing basis. The methodology and presentation of results for the IDMC are covered in the IDMC Charter and in Section 18.

9 Changes to the Planned Analyses in the Clinical Trial Protocol

Not applicable.

10 Protocol Deviations and Analysis Sets

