16.1 Adverse Events

Adverse events will be collected throughout the study and coded using version 19.1 of MedDRA or later.

Treatment-emergent adverse events (TEAEs) are those events that start on or after the day of first administration of study treatment. If an AE started on the same date as the first administration of the first study treatment given, the timing related to study treatment as recorded on the adverse events page of the eCRF will be taken into account when determining treatment emergence. A worst case approach will be used, ie if time is missing or if the AE occurred at the same time as the first administration of the first study treatment given, then the AE will be classified as treatment-emergent.

Incomplete AE-related dates will be handled as follows:

- In case the onset date is missing completely or missing partially but the onset month and year, or the onset year are equal to the start of study treatment then the onset date will be replaced by the minimum of start of study treatment and AE resolution date.
- In all other cases the missing onset day or missing onset month will be replaced by 1.
- Incomplete stop dates will be replaced by the last day of the month (if day is missing only), if not resulting in a date later than the date of subject's death. In the latter case the date of death will be used to impute the incomplete stop date.
- In all other cases the incomplete stop date will not be imputed.

Only TEAEs will be included in tables and will be summarized by treatment arm. All AEs will be listed.

Unless otherwise stated, TEAEs will be displayed in terms of frequency tables: primary SOC in alphabetical order, then PT in order of decreasing frequency across both treatment arms. If a subject has more than one event for a particular SOC or PT, then the event will be counted once only for the subject. For example, if a subject has two different TEAEs but these are within the same SOC, then they will be counted once for each PT but only once for the SOC. If at any time a summary is being prepared on data that are not fully coded, uncoded TEAEs will be summarized with a SOC as 'Uncoded' and the PT term will be set to the TEAE verbatim text.

If an AE is reported for a given subject more than once during treatment, the worst relationship to study treatment will be tabulated.

Adverse events related to study treatment are those events with relationship missing, unknown or yes.

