16.1.1 All Adverse Events

An overall summary table will present the number of subjects with at least one of the following TEAEs, summarized by treatment arm:

- TEAE
- Study drug related TEAE
- Serious TEAE
- Study drug related serious TEAE
- TEAE of NCI-CTCAE toxicity Grade 1
- TEAE of NCI-CTCAE toxicity Grade 2
- TEAE of NCI-CTCAE toxicity Grade 3
- TEAE of NCI-CTCAE toxicity Grade 4
- TEAE of NCI-CTCAE toxicity Grade 5
- TEAE of NCI-CTCAE toxicity Grade ≥ 3
- TEAE of NCI-CTCAE toxicity Grade ≥ 4
- Study drug related TEAE of NCI-CTCAE toxicity Grade 1
- Study drug related TEAE of NCI-CTCAE toxicity Grade 2
- Study drug related TEAE of NCI-CTCAE toxicity Grade 3
- Study drug related TEAE of NCI-CTCAE toxicity Grade 4
- Study drug related TEAE of NCI-CTCAE toxicity Grade 5
- Study drug related TEAE of NCI-CTCAE toxicity Grade ≥ 3
- Study drug related TEAE of NCI-CTCAE toxicity grade ≥ 4
- TEAE of special interest
- TEAE of special interest Grade 1
- TEAE of special interest Grade 2
- TEAE of special interest Grade 3
- TEAE of special interest Grade 4

- TEAE of special interest Grade 5
- Study drug related AESI
- Study drug related AESI Grade 1
- Study drug related AESI Grade 2
- Study drug related AESI Grade 3
- Study drug related AESI Grade 4
- Study drug related AESI Grade 5
- TEAE leading to death
- Study drug related TEAE leading to death.
- Injection Site Reactions

Incidence rates will be included in these overall summaries as the number of events per 100 subject-years of exposure to IMP, calculated as the number of subjects with AEs divided by the total time at risk across all subjects in the given treatment arm, multiplied by 100. Time at risk for a subject is calculated as time from first dose to 28 days following the last dose of IMP. Two-sided 95% CIs for incidence rates will be provided using the exact Poisson method.

The following frequency tables will be prepared by treatment arm, primary SOC in alphabetical order, then PT in order of decreasing frequency across both treatment arms:

- TEAEs
- Study Drug related TEAEs
- Serious TEAEs
- Non-serious TEAEs with frequency of $\geq 5\%$ in any treatment arm
- Non-serious TEAEs with frequency of $\geq 1\%$ in any treatment arm
- TEAE leading to death
- Study drug related TEAE leading to death
- TEAEs by NCI-CTCAE toxicity grade
- Study Drug related TEAEs by NCI-CTCAE grade
- TEAEs by worst NCI-CTCAE toxicity grade.
- Injection Site Reactions- Local Tolerability

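### The TEAE/SAE secondary endpoint ends at Week 52 in three places and at the 4-month visit in Protocol 8.3.2, and the SAP does not say which set of AE tables reports it

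*Protocol*

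**What the plan says.** Four current passages define the endpoint, and they do not agree:

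- Protocol synopsis: "Occurrences of treatment-emergent adverse events (TEAEs) and serious adverse events (SAEs) including and up to Week 52". SAP Section 6 gives the same window.
- Protocol Section 5.2.3.3: "Incidence of TEAEs and SAEs including and up to Week 52".
- Protocol Section 8.3.2: "Occurrences of TEAEs and SAEs including and up to the 4-month Safety Evaluation visit". Its recording schedule adds the 4-week and 4-month follow-up visits.

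The related secondary objective (synopsis and Protocol Section 4.2.2) compares safety up to Week 52. The primary AESI endpoint is also Week 52 throughout. The Amendment 2 list of changes does not mention this window.

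SAP Section 5 says the SAP is built on Protocol Section 8. SAP Section 9 lists no changes from the planned analyses. On data cut-offs, SAP Section 8 says "The final analysis will include all data collected during the study up to week 52 date" (or end of treatment plus 28 days if later, for completers), and then "All AE tables and listings will be re-produced to reflect any additional AEs and any updates to the reported AEs in final analysis".

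On what is counted, SAP Section 16.1 says "Treatment-emergent adverse events (TEAEs) are those events that start on or after the day of first administration of study treatment". It gives no end. On incidence rates, SAP Section 16.1.1 says "Time at risk for a subject is calculated as time from first dose to 28 days following the last dose of IMP".

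**The concern.** Two stated rules give two patient counts for each TEAE and SAE row of one endpoint. The SAP will produce tables close to both rules without saying which set answers the endpoint. The treatment-emergent definition cannot decide it, because it has a start and no end. Since SAP version 3.0 there is a single database lock after the 4-month visit, so both sets come from the same locked data.

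The longer window covers a different kind of time. For completers it adds weeks after study drug, and from the 4-week follow-up visit RA treatment is at the investigator's discretion.

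There is also a fault within the rates. Events per 100 subject-years in the second run would take events up to 4 months after the last dose and divide them by exposure that stops at 28 days.

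**Working it through.** **Inputs**

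- Last dose at Week 48 (Protocol Table 1, note g).
- 4 months after last dose: 16 weeks, or 4 × 30.4375 / 7 = 17.39 weeks with the SAP Section 11.8 conversion.
- Week 52 reference rates: SAEs 15-17%, TEAEs up to 91% (Protocol Section 5.2.3.3).
- 130 patients per arm and 20% dropout (Protocol Section 8.1).
- Event rate after Week 52: not in the documents. Assumed to be r times the earlier rate, with r from 0 to 1.

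**1. The plan's own figure.** Protocol Appendix C gives about 68 weeks from screening to the 4-month visit. 4 + 48 + 16 = 68, so it reproduces. With calendar months it is 4 + 48 + 17.4 = 69.4.

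**2. The two windows for a completer.** Short: Week 52. Long: 48 + 16 = Week 64, or 48 + 17.39 = Week 65.4. The extra time is 12 to 13.4 weeks.

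**3. Effect on each arm's incidence.** With p52 the Week 52 incidence and T the end of the long window:

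p(T) = 1 − (1 − p52)^(1 + r(T − 52)/52)

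| Week 52 incidence | r | Week 64 | Week 65.4 | Rise (points) |
|---|---|---|---|---|
| SAE 15% | 1 | 18.1% | 18.5% | 3.1 to 3.5 |
| SAE 17% | 1 | 20.5% | 20.9% | 3.5 to 3.9 |
| SAE 15% | 0.5 | 16.6% | 16.8% | 1.6 to 1.8 |
| SAE 17% | 0.5 | 18.8% | 19.0% | 1.8 to 2.0 |
| SAE 15% or 17% | 0 | 15% or 17% | 15% or 17% | 0 |
| TEAE 91% | 1 | 94.8% | 95.2% | 3.8 to 4.2 |

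If about 80% of patients contribute the extra time at r = 1, the SAE rise is 0.8 × 3.1 to 0.8 × 3.9, or 2.5 to 3.1 points. At r = 1 with full follow-up it is about 4 to 5 more patients with an SAE per arm (130 × 0.031 = 4.1; 130 × 0.039 = 5.1).

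Patients whose last dose is at or before Week 34.6 to 36 (52 − 17.4, 52 − 16) reach their 4-month visit by Week 52, so the longer window may add nothing for them.

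**4. Effect on the comparison.** With equal event rates both arms move together. As an illustration of unequal arms, 15% and 17% differ by 2.0 points at Week 52 and by 20.9 − 18.5 = 2.4 at Week 65.4. The 95% CI half-width for an arm difference, 1.96 × √(2p(1 − p)/130), is 8.7 points at 15% and 9.1 at 17%.

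**5. Numerator and denominator of the rates.** A completer's time at risk ends at 48 + 4 = Week 52. Re-run tables counting to Week 64-65.4 include 12 to 13.4 weeks of events with no matching exposure. If all patients complete and r = 1, the SAE rate is multiplied by 18.1/15 = 1.21 to 18.5/15 = 1.23.

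For early discontinuers the mismatch is already in the Week 52 tables. SAP Section 8 keeps their data to theoretical Week 52 or the 4-month visit, whichever is first. For a last dose at Week 24, as an illustration, time at risk ends at Week 28 but events count to Week 40-41.4.

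**The case against.** **The longer window may be deliberate.** Protocol 8.3.2 names the 4-week and 4-month visits while the primary endpoint beside it stops at Week 52, and the AE reporting period also runs to the 4-month visit. That stands as a reason not to call Week 52 the only defensible choice. It does not remove the conflict: a reporting period says what is collected, and 8.3.2 defines an endpoint.

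**The SAP is not silent.** Its Section 6 says Week 52, and its Section 8 attaches the Week 52 cut to the final analysis. The CSR is prespecified to cover both periods, there is one lock, and no unblinding may precede SAP approval. The study is descriptive. A reader might infer that the sponsor could pick the more favourable result after unblinding. The documents do not support that much: what is missing is a label on one of two prespecified outputs.

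**A reader might infer that the two results will be 3 to 4 SAE points apart.** No document gives such a difference. It needs the Week 52 rate to continue unchanged off study drug and every patient to be followed. Nor is one arm's standard error a fair yardstick for the gap, because the two counts are nested in the same patients.

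**A reader might infer that the conflict in the outputs persists whatever end is given to treatment-emergent.** It does not. SAP Section 16.1 puts only TEAEs in tables, and SAEs are summarised as serious TEAEs. An end at last dose plus 28 days would close a completer's window at Week 52, and the two sets would nearly coincide.

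**Two supporting arguments carry little weight.** The 91% and 15-17% rates are background, with no comparison against them planned. Off-drug time under investigator-chosen RA treatment also occurs before Week 52 in early discontinuers.

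**Conclusion.** The conflict is real and sits in current text: three passages and the objective say Week 52, Protocol 8.3.2 says the 4-month visit, and the SAP produces both without naming the one that reports the endpoint. The open-ended treatment-emergent definition is part of the cause, and it makes the re-produced incidence rates internally inconsistent.

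The size is modest and conditional. Each arm's SAE incidence would be 3.1 to 3.9 points higher under the longer window if the 15-17% rate continued unchanged and all patients were followed. It would be 0 to 3.9 points higher if the later rate lies anywhere from nil to unchanged. The upper figure would be exceeded only if the rate rose after Week 52. The between-arm difference, which the comparative objective depends on, barely changes. The primary endpoint's window is not in conflict. This should be corrected because safety is the trial's main purpose and the correction is cheap. It does not threaten the trial's conclusions.

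**What to change.** 1. Use one window in the synopsis, Protocol 5.2.3.3, Protocol 8.3.2 and SAP Section 6. Week 52 needs the fewest edits and fits the secondary objective. If the sponsor intends the longer window, the other three passages and the objective must change instead, and the SAP must name the re-produced tables as the endpoint result.
2. With Week 52 chosen, state in SAP Section 8 that the Week 52 tables report the endpoint. Label the 4-month AE output as supplementary follow-up, either cumulative or restricted to events starting after Week 52.
3. In SAP Section 16.1.1, make the events in the incidence rates cover the same period as the time at risk, for early discontinuers as well as completers. Either count only events up to last dose plus 28 days, or extend the time at risk to the end of event counting. An explicit end for treatment-emergent events in Section 16.1 would do much of this.

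The cost is a line in the protocol, a few lines in the SAP, relabelled outputs, and some programming for the rates. No data collection changes. The downside is that events after Week 52 fall outside the endpoint count and appear only as supplementary results.
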